**Austria specific reporting instructions:**

All SAEs have to be documented by the sponsor and immediately reported according to § 42 (8) of the Austrian Medical Device Directive (StF: BGBI. Nr. 657/1996, BGBI. I Nr. 143/2009) to the competent authority (AGES) and the competent authorities of other countries within the European Union where the study is conducted. All SAEs must be reported using the templates provided by AGES.

It is the responsibility of the local investigator to follow the SAE and SADE reporting requirements stipulated by the Investigational Centre's reviewing REC and the Sponsor.

### **11.2.6. Recording and Reporting of Device Deficiencies**

All device deficiencies will be documented throughout the study. The investigator at each site will be responsible for managing all device deficiencies and determine and document in writing whether they could have led to a serious adverse device effect.

All device deficiencies that might have led to a serious adverse device effect(s) if: suitable action had not been taken; intervention had not been made; or if circumstances had been less fortunate, must be reported to the Sponsor as for SAEs/SADEs.

### **11.2.7. Healthcare Arrangements and Compensation for Adverse Events**

Healthcare arrangements for subjects who suffer an adverse event as a result of participating in the study may include advice from clinical members of the study team or the patient's treating diabetes team, or use of emergency health services.

If an adverse event occurs, there are no special compensation arrangements unless this was due to the negligence of one of the clinical investigators or due to harm resulting from study protocol design. In this case subjects may have grounds for legal action for compensation. The normal national complaints mechanism will be available. In addition, any harm arising due to study design (both negligent and non-negligent) will be covered under Sponsor's insurance policy as applicable.

## **11.3. Risks and discomforts and potential / anticipated adverse events and adverse device events/effects**

### **11.3.1. Risks and anticipated adverse events**

Known risks represent hazardous situations which may result in anticipated adverse events. In the following text, where appropriate, the term "risk" and "anticipated adverse events" are used interchangeably without affecting meaning.

### **11.3.2. Hypoglycaemia and hyperglycaemia**

Subjects with type 1 diabetes have a pre-existing risk for hypoglycaemia and hyperglycaemia. Potential risks are:

- Risk of mild to moderate hypoglycaemia and associated symptoms such as sweating, trembling, difficulty thinking and dizziness. There is also a rare risk of severe hypoglycaemia when conscious level is altered, needing help from a third party to correct the hypoglycaemia. These risks are pre-existent in any patient with type 1 diabetes and the study objective is to develop systems to minimise these risks
- Risk of possible mild to moderate hyperglycaemia similar to the risk that a subject with type 1 diabetes experiences on a daily basis
- Risk of hyperglycaemia leading to diabetic ketoacidosis (DKA). This risk is pre-existent in any patient with type 1 diabetes.

### **11.3.3. Blood sampling**

Subjects will be required to have screening blood tests at baseline (venepuncture). Venepuncture is required annually as part of the annual review for people with diabetes, and in some places venepuncture is required every 3 to 6 months for assessment of HbA1c. HbA1c samples collected during the study can be capillary (NOT point of care) or venous samples. Capillary samples can be collected by the participant using their own blood glucose testing apparatus and delivered to the local investigator if required.

Potential risks of venepuncture include:

- Localised infection – an infection in the tissue around the site
- Phlebitis – inflammation of the wall of the vein
- Haematoma – an accumulation of blood within the tissues that clots to form a solid swelling

Local anaesthetic cream or spray may be used to minimise the discomfort.

### **11.3.4. 12-lead electrocardiogram**

Potential risks and adverse device effects associated with electrocardiogram recording:

- Slight discomfort at the time of electrode adhesives placement (rare)
- Mild skin irritation to electrode adhesives (rare)

If an incidental finding is found during the electrocardiogram recording at the Recruitment Visit, this will be referred by the Investigator to the clinical team, to be managed as per local site policy.

### **11.3.5. Finger-prick blood glucose measurements**

Finger-prick tests may produce pain and/or bruising at the site.

### **11.3.6. Insulin pump therapy**

Subjects participating in this study are already using an insulin pump. Potential risks and adverse device effects associated with insulin pump therapy include:

- Slight discomfort at the time of insertion of the insulin delivery cannula (common)
- Slight bruising at the site of insertion (common)
- Bleeding at insertion site (rare)
- Infection at the site of insertion (rare)
- Allergy to the insulin delivery cannula or adhesive (rare)
- Infusion set and cannula occlusions (rare)
- Insulin pump malfunction and mechanical problems (rare)
- Allergy to insulin (very rare)
- Lipodystrophy / lypoatrophy (very rare)
- Priming mechanism failure
- Pump screen damage
- Fast battery drainage

### **11.3.7. Continuous glucose monitoring**

Potential risks and adverse device effects associated with CGM:

- Slight discomfort at the time of insertion of CGM (common)
- Slight bruising at the site of insertion (unlikely)
- Bleeding at insertion site (rare)
- Infection at the site of insertion (very rare)
- Intermittent CGM failure (common)

If a skin reaction is classified as severe (the observation is noticeable and bothersome to the subject and may indicate infection or risk of infection or potentially life-threatening allergic reaction); an adverse event form will be completed.

### **11.3.8. Holter monitor**

Potential risks and adverse device effects associated with Holter monitor:

- Slight discomfort at the time of electrode adhesives placement (rare)
- Mild skin irritation to electrode adhesives (rare)

If an incidental finding is found during analysis of the Holter monitor data at the end of the study period, this will be referred by the Investigator to the clinical team, to be managed as per local site policy.

### **11.3.9. Actiwatch**

Potential risks and adverse device effects associated with Actiwatch include:

- Mild irritation at skin surface in contact with Actiwatch (rare)

### **11.3.10. Human factor assessment**

As part of the study, subjects will complete surveys and participate in focus groups which include questions about their private attitudes, feelings and behaviour related to diabetes. It is possible that some people may find these surveys and focus groups to be mildly upsetting. Similar methods have been used in previous research and these reactions are uncommon.

### **11.3.11. Burdens**

The study will involve up to 19 visits but all of these visits could be done via e-mail/telephone. The study also includes two up to 6 hour visits to the clinical research facility (which can be done via telephone if required) and four months home study period.

At home, subjects will wear the closed-loop system for a 4 month period. The subject is required to carry the closed-loop system for work and when going outside home. During the night, the closed-loop system will be located on a bedside table.

The subjects will be required to perform regular finger stick measurements (4 - 6 hourly) during day time.

### **11.3.12. Risk analysis and residual risk associated with the investigational device**

After in-depth analysis and consideration of all the potential hazards in relation to use of the CamAPS FX system in the home environment, it is concluded that the CamAPS FX system is safe, if used as intended.

Risk Assessment of the CamAPS FX system has been carried out in accordance with ISO 14971:2012. A preliminary Hazard Determination has been carried out including consideration of the questions in Annex C of ISO 14971:2012.

One hazard 'Hazard S7: Incorrect Calibration of Blood Glucose Sensor due to error of reading resulting in overestimation of blood glucose' is the only hazard identified that could not be reduced to an acceptable risk level, post mitigation. Our in-detail risk/benefit assessment concluded that the benefits of the system outweigh the risk with respect to this specific hazard.

As per our risk management process, further risk analysis shall be undertaken post production and release as to ensure any issues raised are acted upon to ensure the CamAPS FX system continues to improve and develop.

## **11.4. Benefits**

It is expected that day and night closed-loop system or sensor-augmented pump therapy may have an important role in the management of diabetes. Therefore, the results of this study are likely to be beneficial for subjects with diabetes.

It is possible that subjects will not directly benefit from being a part of this study. However, it is also possible that the blood sugar information from the CGM devices along with the information about insulin dosing during day and night closed-loop will be useful for subjects' diabetes self-management.

## **11.5. Data and Safety Monitoring Board**

An independent Data and Safety Monitoring Board (DSMB) will be informed of all serious adverse events and any unanticipated adverse device effects that occur during the study and will review compiled adverse event data at periodic intervals.

# **12. Methods and Assessments**

## **12.1. Procedures**

### **12.1.1. Height and weight**

These will be recorded at the study initiation visit at baseline. Height will be measured in centimetres using calibrated measuring devices. Weight will be measured in kilograms using a calibrated electronic scale.

## **12.1.2. Continuous subcutaneous glucose monitoring**

At least 10 days of CGM data will be collected before visit 4. During the study subject is required to upload the CGM data via internet using secure website.

## **12.1.3. Insulin pump data**

During the study subject is required to upload insulin pump data via internet using secure website.

## **12.1.4. 12-lead electrocardiogram**

During the Recruitment Visit, a 12-lead electrocardiogram recording will be collected. Any incidental finding will be referred by the Investigator to the clinical team and be managed as per local site policy.

## **12.1.5. Holter monitor**

At least 5 days of Holter monitor data will be collected during the fourth month in the two treatment groups and analysed at the end of the study period. Any incidental finding will be referred by the Investigator to the clinical team and be managed as per local site policy.

An incidental finding may be defined as 'a finding that has potential health or reproductive importance, unknown to the participant, which is discovered unexpectedly in the course of conducting research, but is unrelated to the purpose and beyond the aims of the study'. This study will adopt the following framework for handling incidental findings:

- To respect the research participant's right to know or, alternatively, their right not to know about incidental findings. Explicit consent must have always been given by the participant for incidental findings to be returned.
- Incidental findings should only be returned where they are of significant clinical importance.
- Incidental findings should be clinically and analytically validated before being returned to participants by their treating clinician.
- Feedback to individual participants should be conducted by a trained professional.

## **12.2. Surveys and focus groups**

Human factors assessments in closed-loop trials are made up of tests and procedures that taps in to the “human side” of these systems. Human factor assessments cut across the acceptability, usability, and efficacy of the system from the perspective of the user. Further, human factor assessments help to understand expectations, attitudes, and behaviours that influence the uptake and response to using a closed-loop system. The human factor assessments in research include both quantitative and qualitative methods and have been tested in adults in the targeted age range. They reflect the most methodologically sound and clinically informed tools available. Surveys are listed in Table 3 and all surveys will be administered in-person. It is estimated that participants will take 20-25 minutes to complete surveys. Surveys will be completed at the time of major assessments in the trial – baseline (after run-in, but prior to randomisation) and at the end of each study period.

In addition, focus groups will be convened during the study trial. Focus groups will meet when each study group completes each study period. We will aim to conduct focus groups in-person and will utilise local facilitators who have worked with the research team on similar projects. Focus groups will include 3-6 participants and a script of open-ended questions will be used to gather feedback and reactions to the closed-loop system, the clinical trial, and quality of life changes. There will also be time for discussion of content raised by participants. Use of a moderator with advanced training (PhD level) will ensure consistency across groups. Sessions will be audio- and video-taped and transcribed by a professional transcription service.

### **12.3. Laboratory methods**

#### **12.3.1. Screening sample**

Renal, liver and thyroid function and anti-transglutaminase antibodies with IgA levels (to exclude diagnosis of coeliac disease) and full blood count will be measured locally if not done within the previous 3 months.

#### **12.3.2. C-peptide and glucose**

A random blood sample for the measurement of C-peptide with simultaneous exclusion of biochemical hypoglycaemia (plasma glucose <4.0 mmol/l (72mg/dl)) by laboratory glucose analysis on a sample at the same time point, will be taken at screening.

Plasma C-peptide will be measured at a local laboratory.

#### **12.3.3. HbA1c**

HbA1c will be measured at a local laboratory compliant with IFCC reference HbA1c method. This sample can be capillary or venous.

## **12.4. Total Blood Loss**

The total blood loss will be approximately 50 to 100 ml.

# **13. Study Materials**

## **13.1. Insulin**

U-100 rapid acting insulin analogue will be used in the insulin pumps. This includes either Aspart (Novorapid; Novo Nordisk, Bagsvaerd, Denmark), Faster Insulin Aspart (Fiasp; Novo Nordisk, Bagsvaerd, Denmark), or Lispro (Humalog; Eli Lilly, Indianapolis, USA) but not Glulisine (Apidra; Sanofi-Aventis, Paris, France).

## **13.2. Insulin Pump**

During the run-in period and both study arms, the Dana insulin pump (SOOIL) will be used. Glooko/Diasend software or similar will be used to download insulin pump data at regular intervals.

## **13.3. Continuous Subcutaneous Glucose Monitor**

The Dexcom G6 real-time sensor with sensor applicator (Dexcom, Northridge, CA, USA) will be the study CGM. The sensor will be calibrated according to manufacturer's instructions.

## **13.4. Blood Glucose Meter**

Study participants will use their own approved glucose meter for self-monitoring of capillary blood glucose (SMBG) during the study. The capillary glucose meter readings may be used to calibrate the sensor according to manufacturer's instructions.

## **13.5. Computer-based Algorithm**

The model predictive computer-based controller will be used. The controller has been used safely and effectively in the closed-loop studies in both children and adults with T1D (studies REC Ref. 06/Q0108/350, REC Ref. 07/H0306/116, REC Ref. 08/H0304/75, REC Ref. 08/H0308/297, REC Ref. 09/H0306/44, REC Ref. 10/H0304/87, REC Ref. 12/EE/0155, REC Ref. 12/EE/0034, and REC Ref. 12/EE/0424).

## **13.6. Actiwatch**

An Actiwatch (Philips Respironics, Bend, Oregon, USA), worn on the non-dominant wrist, will be used to measure sleep.

## **13.7. Holter Monitor**

A Holter monitor (Lifecard 12; Spacelabs Healthcare, Hertford, UK, or similar) will be applied.

# **14. Data Analysis**

## **14.1. Primary Analysis**

The primary analysis will evaluate the time (midnight to midnight) spent in the target glucose range from 3.9 to 10 mmol/l (70 to 180mg/dl) based on CGM glucose levels during the 16 week interventions.

## **14.2. Secondary Analysis**

### **14.2.1. Biochemical evaluation**

Key secondary endpoints include the between group differences in time spent above target glucose (>10.0 mmol/l) (>180mg/dl), average glucose levels, HbA1c levels at the end of treatment period and time spent below target glucose (<3.9mmol/l) (<70mg/dl). Other secondary efficacy endpoints include the between group differences in standard deviation, and the coefficient of variation of glucose levels, the time with glucose levels < 3.5 mmol/l (63mg/dl) and <3.0 mmol/l (54mg/dl), the time with glucose levels in the significant hyperglycaemia (glucose levels > 16.7 mmol/l) (300mg/dl), total, basal and bolus insulin dose.

All analyses will be by intention to treat.

Summary statistics for the following outcome metrics will also be tabulated separately for daytime (defined as 6am to less than 12am) and nighttime (defined as 12am to less than 6am) over the four month period:

- Percent time with glucose levels spent in the target range (3.9 to 10.0 mmol/L)
- Mean of glucose levels
- Standard deviation of glucose levels
- Percent time with glucose levels below 3.9 mmol/L
- Total insulin dose

Per-protocol analysis will also be performed which will evaluate glucose sensor based outcomes with a minimum of 60% of available CGM readings during the control period and 60% CL system use during the CL period. Descriptive tabulations of questionnaires will be carried out.

#### **14.2.2. Analysis of Human Factors Data**

Quantitative data on usability and satisfaction will be analysed using simple descriptive statistics. In addition, we will analyse scores from the measures in the human factors assessment battery to determine if changes occur over time and between groups. Using SAS v9.4, we will construct predictive models in the general linear framework to examine each set of human factors (e.g., QOL, fear of hypoglycaemia) and its association with our outcomes. Group assignment will be the primary covariate.

Qualitative data will be analysed using Atlas.ti (release 6.0; Scientific Software Development GmbH, Berlin, Germany) to organise and manage the entire corpus of focus group data. Analysis begins with an initial coding procedure to capture and describe the range of responses to the intervention. A second, more focused and detailed level of coding will be applied to major categories of findings in the initial review to determine themes in response to the clinical trial, use of the closed-loop system, and quality of life changes.

#### **14.2.3. Cardiac Arrhythmia Analysis**

Holter monitor data at the fourth month in the two treatment groups will be analysed at the end of the study period. Arrhythmic events analysed will include atrial fibrillation, atrial ectopic beats, bradycardia, ventricular premature beats, complex ventricular premature beats, non-sustained ventricular tachycardia and measures of heart rate variability and QT interval. All identified arrhythmic events will be manually verified for accuracy.

Investigators will be blinded to glucose values during arrhythmia analysis. The frequency of arrhythmic events during periods of hypoglycaemia (sensor glucose  $\leq 3.9$  mmol/L and 3.0 mmol/L), will be compared to the frequency of arrhythmic events during normoglycaemia (3.9-10 mmol/L) within each study arm. Analyses will be calculated for daytime and night-time periods to take into account diurnal variation. Any incidental finding will be referred by the Investigator to the clinical team and be managed as per local site policy.

#### **14.2.4. Quality of Sleep Assessment using Actiwatch**

Sleep will be automatically scored by Actiware software using previously described and validated algorithms. Sleep duration will be calculated as the sum of all epochs scored as sleep during the time in bed. Variability across nights in a participant's sleep duration will be summarised using the coefficient of variation. Sleep data will be averaged across nights in each participant for each study period.

### **14.3. Exploratory Analysis**

No exploratory analyses will be performed.

### **14.4. Interim Analysis**

No interim analysis will be performed.

### **14.5. Statistical Methods**

The respective values obtained during the 4 month randomised interventions contrasting the closed-loop system against the sensor augmented insulin pump therapy will be compared using a linear mixed model adjusting for period as a fixed effect and site as a random effect. The analysis dataset will be three records per subject (one for baseline and one for each period). Inclusion of the pre-randomization baseline value as a third observation for each subject in the model gives a variance reduction analogous to adjusting for it as a covariate. Residual values from the regression model will be examined for an approximate normal distribution. If values are highly skewed a transformation or nonparametric analyses will be used. The statistical analysis will include the assessment of the period effect.

The primary analysis will follow the intention-to-treat principle and will be a single comparison. No attempt will be formally made to control the overall type I error rate for the secondary outcomes. A 5% significance level will be used to declare statistical significance for the primary comparison.

For the primary endpoint and key secondary endpoints, the familywise type I error rate (FWER) will be controlled at two-sided  $\alpha = 0.05$ . A gatekeeping strategy will be used, where the primary endpoint will be tested first, if passing the significance testing, other key endpoints will be tested in the order listed below using the fixed-sequence method at  $\alpha = 0.05$ :

- Time spent with sensor glucose levels between 3.9 to 10.0 mmol/l

- Time spent above target glucose (10.0 mmol/l)
- Average of glucose levels
- HbA1c
- Time spent below target glucose (3.9 mmol/l)

This process continues iteratively moving to the next variable down on the list until a non-significant result ( $p \geq 0.05$ ) is observed, or all five variables have been tested. If a non-significant result is encountered, then formal statistical hypothesis testing is terminated and any variables below on the list are not formally tested and analysis of these variables becomes exploratory.

A per protocol analysis will be performed to replicate the primary analysis limited to subjects who meet the following criteria:

- Intervention period: Closed loop active for at least 60% of the time
- Control period: Sensor used for at least 60% of the time

Consistency of treatment effect across sites will be investigated by testing for interaction between study intervention and study site.

Severe hypoglycaemic events and ketone-positive hyperglycaemia will be tabulated in each treatment group, which will be compared (if enough events) using repeated measures logistic regression adjusting for period and whether the subject has ever had a prior event. We will also apply a repeated measures regression model as for the primary analysis to assess treatment differences in absolute terms.

Safety data including severe hypoglycaemia events and ketone-positive hyperglycaemia will be tabulated for all subjects, including drop-outs and withdrawals, irrespective of whether CGM data are available and irrespective of whether closed-loop was operational.

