42 power, a treatment effect of 10% in the percentage of time in the target range, and a standard
43 deviation of 18% for an individual measurement.

44 **4. Outcome Measures**

45 **Primary Efficacy Endpoint:**

46 • Time spent in the target range (3.9 to 10.0 mmol/L) over the 16 week period

47 **Key Secondary Endpoints:**

48 • Percent time spent with glucose levels above 10.0 mmol/L
49 • HbA1c at 16 weeks
50 • Mean of glucose levels
51 • Percent time spent with glucose levels below 3.9 mmol/L

52 **Secondary Efficacy Endpoints:**

53 *CGM Metrics*

54 Glucose variability

- Standard deviation of glucose levels
- Coefficient of variation of glucose levels

57 Hyperglycemia

- Percent Time spent with glucose levels above 16.7 mmol/L

59 Hypoglycemia

- Percent Time spent with glucose levels below 3.5 mmol/L
- Percent Time spent with glucose levels below 3.0 mmol/L

62 *Insulin Delivery*

- Total insulin dose (units/kg/day)
- Basal insulin dose (units/kg/day)
- Bolus insulin dose (units/kg/day)

66 *Questionnaires*

- WHO-5 quality of life measurement
- Diabetes Distress Scale
- Glucose Monitoring Satisfaction Survey
- Hypoglycemia Confidence
- INSPIRE Survey
- Pittsburgh Sleep Quality Index (PSQI)

73 *Cognitive testing (CogState)*

- Detection Task Score
- Identification Task Score
- One Card Learning Task Score
- One Back Task Score

78 *Actiwatch data*

79 *Holter data*

80 **4.1 Calculation of CGM Metrics**

81 For the primary outcome and all secondary CGM metrics, a single value will be calculated for
82 each subject for each period by pooling all CGM readings between the treatment initiation visit
83 and up to 112 days post-initiation visit or the end of treatment visit, whichever comes first. All
84 glucose sensor readings will be weighted equally in the pooled percentages regardless of how
85 they distribute across weeks. Data will not be truncated due to protocol deviations.

86 Baseline CGM metrics will be calculated by pooling all readings up to the last 14 available days
87 of CGM readings prior to randomization.

88 **5. Analysis Datasets and Sensitivity Analyses**

89

90 **5.1 Analysis Cohorts**

91 The primary analysis and all secondary analyses will be performed on an intention-to-treat basis
92 with each day included in the treatment group assigned by randomization.

93 A per-protocol analysis restricted to randomized participants with a minimum of 60% of

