94 available CGM readings during the control period and 60% CL system use during the CL period
95 will be conducted for the primary outcome.

96 Safety outcomes will be reported for all enrolled participants, regardless of whether the study
97 was completed.

98

99 **6. Analysis of the Primary Endpoint**

100

101 **6.1 Included Subjects**

102 Only subjects with at least 168 hours of CGM data in at least one period will be included. If a
103 subject has more than 168 hours of data in period 1 and then drops out of the study without any
104 data in period 2, then he or she will be included in the analysis.

105 **6.2 Missing Data**

106 Missing data will not be imputed for the primary analysis in this study.

107 **6.3 Statistical Methods**

108 Mean \pm SD or summary statistics appropriate to the distribution will be reported for the primary
109 outcome and each of the key secondary outcomes listed below over the 16 week period by
110 treatment intervention. The treatment interventions will be compared using a linear mixed model
111 adjusting for period as a fixed effect and site as a random effect. The analysis dataset will be
112 three records per subject (one for baseline and one for each period). Inclusion of the pre-
113 randomization baseline value as a third observation for each subject in the model gives a
114 variance reduction analogous to adjusting for it as a covariate. Baseline is not modeled as a
115 covariate in this analysis because there is no corresponding baseline for period 2, only pre-
116 randomization. Note that adjusting for a post-randomization period 2 baseline can introduce a
117 bias so that is not done here. The model will account for correlated data from the same subject.

118 A 95% confidence interval will be reported for the difference between the interventions based on
119 the linear mixed model.

120 Residual values will be examined for an approximate normal distribution. If values are highly
121 skewed, then a ranked normal score transformation will be used instead. However, previous
122 experience suggests that the primary outcome will follow an approximately normal distribution.
123 A two-sided p-value will be reported.

124 For the primary endpoint and other key endpoints listed in section 4, the familywise type I error
125 rate (FWER) will be controlled at two-sided $\alpha = 0.05$. A gatekeeping strategy will be used, where

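### Does the unnamed covariance structure for the three-record mixed model leave the primary analysis undetermined?

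*Protocol*

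**What the plan says.** Protocol 14.5 sets out a "linear mixed model adjusting for period as a fixed effect and site as a random effect", with one baseline record and one record for each period. It states that including the "baseline value as a third observation for each subject in the model gives a variance reduction analogous to adjusting for it as a covariate". SAP 6.3 repeats this and the justification, a "variance reduction analogous to adjusting for it as a covariate". It explains that baseline is not a covariate because period 2 has no pre-randomisation baseline of its own, and adds: "The model will account for correlated data from the same subject". Neither document goes further on the covariance structure, the degrees of freedom, or the treatment and period values of the baseline record.

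Four other places bear on the point:

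- **SAP 4.1, length of the records.** Each period value pools readings from initiation "and up to 112 days post-initiation visit or the end of treatment visit, whichever comes first". For baseline, "Baseline CGM metrics will be calculated by pooling all readings up to the last 14 available days" before randomisation.
- **SAP 6.1, incomplete subjects.** A subject is kept if the "subject has more than 168 hours of data in period 1 and then drops out of the study without any" period 2 data.
- **SAP 3, planning SD.** This is a standard "deviation of 18% for an individual measurement"; no correlation is given.
- **SAP 7.4.3, HbA1c.** Baseline, period 1 and period 2 are listed as three separate time points.

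**The concern.** In a parallel-group trial, baseline explains between-subject variation that would otherwise sit in the treatment comparison. In a crossover the subject is already his or her own control, so that variation has gone before baseline is used. A precision gain stated as fact therefore looks like an argument carried over from another design.

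The second worry is practical. If the analyst fits only a random subject intercept (compound symmetry), the residual variance is averaged over all three pairs of records, two of which involve a baseline of at most 14 days. If baseline behaves differently from the 112-day periods, the reported standard error is wrong even though the estimate is right. The primary confidence interval, its p-value and the CGM steps of the fixed sequence all use that standard error. An unstructured fit is equally compatible with the text and gives a different interval.

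**Working it through.** **The plan's own figure.** Protocol 14.6 gives 31 subjects for 10 points, SD 18, 80% power and two-sided 0.05. For a crossover, n = (1.960 + 0.842)² × 2 × 18² × (1 − ρ) / 10² = 50.9 × (1 − ρ). This gives 51 at ρ = 0 and 31 at ρ = 0.40. The figure therefore needs a correlation that the documents do not state. That does not show 31 to be wrong, but it means every correlation below is an assumption.

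**Does baseline add precision?** With complete data and baseline as its own time level, the treatment estimate is half the difference between sequences in mean (Y1 − Y2). Baseline Y0 helps only if cov(Y0, Y1) differs from cov(Y0, Y2).

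- Equal correlations of 0.4, n = 36: SE = √(648 × 0.6 / 36) = 3.286 with two records, and 3.286 with three. The gain is 0%.
- Correlation decaying with time (AR(1)) at 0.6, covariance known: SE falls from 2.683 to 2.544, a variance gain of 1 − (2.544/2.683)² = 10.1%. At 0.4 and 0.8 the gains are 5.4% and 15.1%.
- Four of 36 subjects with period 1 only, equal correlations: variance gain 0.7% (ρ = 0.4) to 2.2% (ρ = 0.8). With eight of 36 it is 1.5% to 4.7%.

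So the sentence is true in some settings and empty in others. In none of these does the baseline record cost precision when the covariance is known.

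**What a compound-symmetry fit does to the standard error.** Write CL for closed-loop and control for sensor-augmented pump. Then reported SE / true SE = √(mean of the three pairwise difference variances / variance of CL − control). SD 18 comes from Protocol 14.6 and SAP 3. The period SDs of 10.6 (CL) and 14.2 (control) are from the 12-week adult study in Protocol 4.9, which Protocol 14.6 cites for the effect. Type I error was simulated with 18 subjects per sequence and 69 df.

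| SD: baseline / CL / control | Correlation: baseline–CL / baseline–control / CL–control | Pairwise variances, same order | SE ratio | Type I error |
|---|---|---|---|---|
| 18 / 18 / 18 | 0.5 / 0.5 / 0.5 | 324, 324, 324 | 1.00 | 5% |
| 18 / 18 / 18 | 0.5 / 0.7 / 0.5 | 324, 194.4, 324 | 0.93 | 7% |
| 18 / 18 / 18 | 0.7 / 0.7 / 0.5 | 194.4, 194.4, 324 | 0.86 | 9% |
| 18 / 18 / 18 | 0.5 / 0.5 / 0.7 | 324, 324, 194.4 | 1.20 | 2% |
| 18 / 10.6 / 14.2 | 0.5 / 0.7 / 0.5 | 245.6, 167.8, 163.5 | 1.08 | 3.5% |
| 18 / 10.6 / 14.2 | 0.7 / 0.7 / 0.5 | 169.2, 167.8, 163.5 | 1.01 | just under 5% |
| 18 / 10.6 / 14.2 | 0.5 / 0.5 / 0.7 | 245.6, 270.0, 103.3 | 1.41 | under 1% |
| 14.2 / 10.6 / 14.2 | 0.5 / 0.7 / 0.5 | 163.5, 121.0, 163.5 | 0.96 | 6% |
| 14.2 / 10.6 / 14.2 | 0.7 / 0.7 / 0.5 | 103.3, 121.0, 163.5 | 0.89 | 8% |

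An analysis of the two period records alone stays at about 5% throughout. Inflation requires a baseline of at most 14 days to track the 112-day periods more closely than they track each other, without a larger variance to offset it. A noisier or more weakly correlated baseline makes the fit conservative.

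**Effect at the planned difference.** With all SDs 18, the statistic for 10 points is:

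- 0.7/0.7/0.5: reported SE √(237.6/36) = 2.57, giving 3.89; true SE 3.00, giving 3.33.
- 0.5/0.5/0.7: reported SE √(280.8/36) = 2.79, giving 3.58; true SE 2.32, giving 4.30.

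All are well above the critical values of 1.995 (69 df) and 2.032 (34 df). Power depends mainly on the CL–control correlation. At 0.5 throughout it is about 90% for the two-record analysis and 91% for compound symmetry. At AR(1) 0.3 it is about 78% and 76 to 77%.

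**Baseline coding.** If baseline were coded as control and also given the period 1 level, each point by which mean baseline exceeds control would lower the estimate by 0.40 points. With its own level the shift is 0. Both documents count the baseline record apart from the two period records, and SAP 7.4.3 treats it as a separate time point, so the first coding is a strained reading.

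**What prescribing a structure would buy.** An unstructured REML fit with Kenward-Roger df held type I error at 5.1 to 5.4% with complete data. Its true SE exceeded that of the two-record analysis by 3.1 to 3.3% in five settings and by 1.5% at AR(1) 0.3. It was 2.3% and 4.7% smaller at AR(1) 0.6 and 0.8. Power at 0.5 throughout was 88.0% against 89.9%. The estimate also moves with chance baseline imbalance between sequences (median shift 0.3 to 0.6 points).

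**The case for a change.** The best case for a change is this. Two fits that both satisfy SAP 6.3 give different intervals, and the unstructured one also gives a different estimate. The trial is open-label, so the structure should not be picked after the data are seen. The same model serves the other CGM, insulin and questionnaire outcomes, where effects may be smaller and a misstated standard error more likely to matter. Three sentences would settle it.

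Much of that stands. The variance-reduction sentence is too broad, the structure is open, and compound symmetry is not safe in every setting. What does not follow is a defect in the planned inference. The documents give no correlations, so neither the size nor the direction of any error can be established, and the 9% figure falls to just under 5% once 10.6 and 14.2 replace 18 for the period SDs. Nor is there one plainly better structure to require: the unstructured fit loses precision against the two-record analysis in six of the eight settings run and would need a fallback if it did not converge with a random effect for four sites.

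**Conclusion.** The observation is right but calls for no change. The baseline sentence is a rationale, not an instruction, and making it conditional would alter no result. The operative commitment, to model the correlation between a subject's records, is in SAP 6.3. The remaining choices are ordinary ones. An analyst who sees a baseline of at most 14 days beside two 112-day periods would give baseline its own time level, check whether its variance and correlations match those of the periods, and choose the covariance and df to suit. The two-record comparison is an available benchmark that holds 5%.

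On size: under assumed correlations, a poorly chosen compound-symmetry fit could have type I error anywhere from under 1% to about 9%, and the documents cannot say where in that range. With baseline as its own level and complete data, the compound-symmetry estimate is the ordinary crossover estimate. At the planned 10-point effect, the choice between compound symmetry and two records moves power by about one to two points at 0.5 throughout and at AR(1) 0.3. These figures rest on 36 subjects split equally between sequences, normal data and the SDs shown.
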